Research Protocol

Official Title: The effectiveness of a patient-navigation-based preoperative rehabilitation exercise program in patients undergoing total knee arthroplasty: a randomised controlled trial

NCT number: NCT07047079

Version Number: Version 1.2

Version Date: May 6, 2025

Document date: July 2, 2025

1. Study design

This study is a prospective, single-centre, superiority randomised controlled trial (RCT) involving two parallel groups. Participants were recruited from among patients newly admitted to the orthopaedic ward who met the selection criteria.

2. Participants

A total of 84 participants were consecutively recruited from among patients newly admitted to the orthopaedic ward who met the selection criteria.

2.1. Participant selection criteria

Inclusion Criteria: (i) patients diagnosed with knee osteoarthritis who are undergoing primary unilateral total knee arthroplasty; (ii) aged between 45 and 90 years; (iii) assessed by the attending physician as having sufficient physical capacity to tolerate preoperative rehabilitation exercises and adequate communication skills to cooperate with all examinations and assessments; and (iv) informed consent was obtained from the patient, and the signed informed consent form was duly completed.

Exclusion Criteria: (i) patients who are uncooperative due to impaired consciousness, cognitive dysfunction, or other factors; (ii) presence of severe concurrent comorbidities, including liver cirrhosis, respiratory failure, renal failure, malignancy, or trauma; (iii) a history of significant neuromuscular disorders or other joint diseases, as determined by the attending physician, that impair knee joint function; (iv) a time interval of greater than 7 days or less than 3 days between the admission day date and the scheduled surgery date; and (v) patients who have undergone systematic lower limb functional training within the past four weeks.

2.2. Sample size

This study used knee osteoarthritis severity as the primary outcome measure. Given the lack of prior research on the effect of patient navigation mode on patients' knee osteoarthritis severity. Therefore, the sample size calculation for the present study was based on the results of the pre-experiment, which showed an effect size of 0.8 on knee osteoarthritis severity. To achieve a statistical power of 0.80 and an alpha level of 0.05, a sample size of 33 participants per group is required. Considering a 20% attrition rate, the total estimated sample size is 84 participants, with 42 participants per group.

3. Randomization and blinding

A non-research team member randomly selected an initial starting point from a pre-generated computerised random number table. From this point, the corresponding random numbers were sequentially identified, ranging from 1 to 84. After sorting the random numbers, participants were randomly assigned in a 1:1 ratio to either Group 1 (the experimental group) or Group 2 (the control group). Group assignments were concealed within 84 consecutively numbered, identical, opaque, and sealed envelopes, which the non-research team member securely kept. On the day of participant enrolment, after completing demographic and clinical data collection, as well as baseline assessments, the principal researcher (recruiter) retrieved the envelope corresponding to the participant's sequential number from the custodian. The envelope was opened, and the participant was assigned to the designated group.

Due to the nature of the intervention, the experimental group received exercise guidance from navigator, while the control group did not. Consequently, blinding of participants, recruiters, or research intervention staff was not feasible. However, outcome assessors and data entry analysts will be blinded. The outcome assessor is an independent research assistant who remained unaware of the allocation status throughout the study. Before the

study, the principal researcher (recruiter) trained the outcome assessor. The outcome assessor independently assessed outcomes and collected data for both groups from T0 to T4. Moreover, the principal researcher (recruiter) instructed all participants not to disclose their group assignment to the outcome assessor. Furthermore, two research assistants, who were not involved in the study process, served as data entry analysts. The group assignment was concealed from these analysts by using coded group identifiers (Group 1 and Group 2) to ensure blinding.

4. Intervention

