6.1. Primary outcome

The primary outcome is the change in knee osteoarthritis severity from admission day (baseline, T0) to surgery day (preoperative) (T1). As the intervention in this study aims to enhance patient adherence to preoperative rehabilitation exercises, the ultimate objective is to improve their rehabilitation outcomes. Therefore, the change in knee osteoarthritis severity from T0 to T1 in both groups of participants will be used to evaluate the effectiveness of the intervention.

Knee osteoarthritis severity will be measured using the Chinese version of the Western Ontario and McMaster Universities Osteoarthritis Index (WOMAC) Scale, which is a self-administered instrument specifically developed to assess the severity of knee osteoarthritis and the efficacy of related treatments (Bellamy et al., 1988). The scale consists of 24 items divided into three subscales: pain (5 items), stiffness (2 items), and physical function (17 items). Several scoring methods have been developed for the Western Ontario and McMaster Universities Osteoarthritis Index Scale items (Noyes, 2016). In this study, a 5-point Likert scale is employed, where 0 represents “no difficulty” and 4 represents “extreme difficulty”. The total score ranges from 0 to 96, with higher scores reflecting more severe knee osteoarthritis.

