Knee range of motion (ROM) will be measured with a goniometer. ROM measurement assesses knee movement amplitude, serving as a critical indicator of knee joint function and a key indicator for evaluating rehabilitation outcomes following total knee arthroplasty. Normal knee range of motion values are as follows: flexion, 0°–135°; extension, 0° (some individuals may exhibit hyperextension of 0°–10°); active range, 0°–135°; and passive range, up to 150°.

Pain intensity will be measured using the Visual Analogue Scale (VAS). The VAS consists of a 10-centimetre horizontal line divided into 10 equal intervals, where higher scores represent greater pain intensity. A score of 0 denotes no pain, whereas a score of 10 denotes the most severe pain imaginable. Patients are instructed to mark the point on the line corresponding to their perceived pain intensity.

7. Statistical analysis

IBM® SPSS Statistics 27.0 will be used to analyse the data from all randomised participants. Statistical significance was set at $p \leq 0.05$. Categorical variables (e.g., gender, marital status, payment type) appeared as frequencies and percentages. Continuous variables (e.g., age, height, weight) appeared as mean \pm standard deviation (SD). Continuous data meeting the assumptions of normality and homogeneity of variance were analysed using independent-sample t-tests; otherwise, the Wilcoxon signed-rank test appeared. Categorical data were analysed using the chi-square test or Fisher's exact test for intergroup comparisons. Generalised Estimating

Equations (GEE) were employed to compare longitudinal changes in outcome variables between groups, with statistical significance set at $p < 0.05$ (two-tailed). The GEE was chosen as it accounts for within-subject correlations inherent in repeated measures, thereby improving the efficiency of parameter estimation in longitudinal analyses. Moreover, the GEE approach flexibly accommodates missing data. When the proportion of missing data was below 5%, the GEE inherently accommodated the missing values; otherwise, multiple imputation procedures were applied.

8. Trial monitoring

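### The stated inputs (effect size 0.8, power 0.80, alpha 0.05) give 26 per group by two-sided t-test, not the 33 that Section 2.2 says are required

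*Combined protocol and SAP*

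**What the plan says.** Section 2.2 (Sample size) of the combined protocol and SAP bases the calculation on a pre-experiment "which showed an effect size of 0.8 on knee osteoarthritis severity". It continues: "To achieve a statistical power of 0.80 and an alpha level of 0.05, a sample size of 33 participants per group is required". It then allows for loss to follow-up: "Considering a 20% attrition rate, the total estimated sample size is 84 participants, with 42 participants per group".

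Section 2.2 gives no test, sidedness, type of effect size, SD or software. The other sections supply part of the context:

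- Section 3 sets two groups at 1:1.
- Section 6.1 defines the primary outcome as the change in WOMAC total score (0 to 96) from T0 to T1.
- Section 7 says that continuous data meeting normality and equal-variance assumptions "were analysed using independent-sample t-tests; otherwise, the Wilcoxon signed-rank test appeared". It also assigns longitudinal comparisons between groups to GEE, at a two-tailed 0.05 level.

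**The concern.** For a two-group comparison of means, effect size, power, alpha and sample size are tied together: any three fix the fourth. Section 2.2 states all four, so the statement can be checked, and on the ordinary reading the four do not agree. The 33 is too large for the stated inputs.

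This paragraph is the only justification for the size of the trial, and it rests on one pilot figure. If 33 is right, then the effect size, the power or the method differs from what is written. If the inputs are right, 33 is not the number required. Either way, the stated basis for 84 cannot be verified.

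**Working it through.** **Inputs.** Effect size 0.8, power 0.80, alpha 0.05 and attrition 20% (Section 2.2); allocation 1:1 (Section 3); continuous change score (Section 6.1); two-sided testing (Section 7). *Assumption:* 0.8 is Cohen's d, the between-group difference in mean change divided by the SD of the change.

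**1. The attrition step reproduces.** 33/(1 − 0.20) = 41.25, rounded up to 42 per group, 84 in total.

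**2. The 33 does not reproduce at d = 0.8.**

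Normal approximation: n = 2(1.960 + 0.842)²/d² = 2 × 7.849/0.64 = 24.53, so 25 per group.

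t-test: find the smallest n at which a noncentral t with 2n − 2 degrees of freedom and noncentrality d√(n/2) gives power 0.80. The solution is 25.52, so 26 per group. As a check, power is 0.791 at n = 25 and 0.807 at n = 26.

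Rank-sum test: Section 7 names the signed-rank test as the fallback, but for two independent groups the corresponding test is the rank-sum. Two routes are usual:

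- Divide the t-test n by an asymptotic relative efficiency (ARE): 25.52/(3/π) = 26.73, so 27; or, with the minimum ARE, 25.52/0.864 = 29.54, so 30.
- Noether's formula, with p = Φ(0.8/√2) = 0.7142: n = 7.849/[6(p − 0.5)²] = 28.51, so 29.

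| Method, d = 0.8, power 0.80 | n per group | Total after 20% attrition | 84 exceeds it by |
|---|---|---|---|
| Normal approximation, two-sided | 25 | 64 | 20 |
| t-test, two-sided | 26 | 66 | 18 |
| Rank-sum, ARE 3/π | 27 | 68 | 16 |
| Rank-sum, Noether | 29 | 74 | 10 |
| Rank-sum, minimum ARE | 30 | 76 | 8 |

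A one-sided t-test needs 20.03, so 21, which is further from 33.

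**3. What 33 per group delivers (two-sided t-test).**

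| n per group | Power at d = 0.8 | Smallest d with 80% power |
|---|---|---|
| 26 | 0.807 | about 0.8 |
| 33 | 0.893 | 0.70 |
| 42 | 0.952 | 0.62 |

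**4. Inputs that would lead to 33.** Each needs something that Section 2.2 does not state:

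- *Attrition counted twice.* 26/0.80 = 32.5, so 33; then 33/0.80 = 41.25, so 42.
- *Power near 90%.* At d = 0.8 and power 0.90, the normal approximation gives 32.84, so 33; the t-test gives 33.83, so 34.
- *A smaller effect.* At d = 0.70 and power 0.80, the normal approximation gives 32.04, so 33; the t-test gives 33.02, so 34.
- *A rounded effect with a conservative rank-sum formula.* At d = 0.75, Noether's formula gives 32.04, so 33. With the minimum ARE, d between about 0.756 and 0.767 gives 33. Rounding alone is not enough for a t-test: d = 0.75 gives 28.90, so 29.
- *A different SD.* If 0.8 is scaled on the single-visit SD and the change is tested, the effect on the change is 0.8/√[2(1 − ρ)], where ρ is the T0–T1 correlation. The t-test solution is then 35.3 at ρ = 0.3, 30.4 at ρ = 0.4 and 25.5 at ρ = 0.5. It rounds up to 33 only for ρ between about 0.35 and 0.37.

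**The case against.** The strongest reply is that the t-test reading is not the only one the plan allows. Section 7 attaches the two-tailed level to GEE, and the t-test sentence follows a description of baseline variables such as age and weight. Section 2.2 speaks of an effect on severity, not on the change in severity. If 0.8 was scaled on the single-visit SD, a GEE contrast of the T0 to T1 change needs a number that depends on ρ. By normal approximation this is 34.3 at ρ = 0.3, 29.4 at 0.4 and 24.5 at 0.5, and it rounds up to 33 for ρ of about 0.33 to 0.35. On this view the 33 is unexplained rather than wrong.

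This stands in part. The effect-size definition is indeed unstated, and the figure of 26 is conditional on reading 0.8 as d for the change. But this route reaches exactly 33 only in a narrow range of a correlation that appears nowhere in the documents. If it was used, the paragraph omits the input that determines its answer, and the remedy is the same.

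It is also fair to say that the practical harm is small. The error, if it is one, adds power, and nothing in conduct or analysis depends on it. Likewise, the double attrition in step 4 fits both 33 and 42 exactly, but no text supports it, and it should not be presented as what happened.

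**Conclusion.** The concern holds. With 0.8 read as Cohen's d on the change score and two-sided testing at 0.05, the stated inputs require 26 per group by t-test and 25 to 30 across the usual two-sided methods, against 33 stated. The effect size, power and sample size in Section 2.2 therefore do not agree as written.

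The direction is conservative. If 20% are lost, the 33 who remain in each group give about 89% power at d = 0.8. The apparent excess of 18 patients over 66 (27%) applies only if 0.8 is exact, is on the SD of the change, and a t-test was meant. If the real target was 90% power, or the real effect 0.70, the excess is about zero. The documents do not show which explanation is true; only the original calculation can.

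**What to change.** Retrieve the original calculation and rewrite Section 2.2 to state the test, the sidedness, the definition of the effect size (which outcome and which SD), the effect size to two decimals and the target power. If the calculation was built on GEE or on a single-visit SD, state the assumed T0–T1 correlation too. The test named should match the primary analysis in Section 7.

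If the stated inputs prove to be the true ones, suitable wording is: *26 evaluable participants per group are required for 80% power at d = 0.8 (two-sided alpha 0.05, t-test). 42 per group are randomised; with 20% attrition, 33 evaluable per group give about 89% power at d = 0.8, or 80% power at d = 0.70.* If another test, power, effect size or SD was used, state that instead.

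Keep enrolment at 84. The cost is one look-up and one reworded paragraph, with no change to enrolment, randomisation or analysis.

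### The allocation appears to be one list of 84 with 42 per arm, opened one envelope at a time by the unblinded recruiter, so the last few allocations could be partly foreseen; the risk is small and cheap to reduce

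*Combined protocol and SAP*

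**What the plan says.** Section 2.2 sets the target: "the total estimated sample size is 84 participants, with 42 participants per group". Section 3 describes how the list was made. A person outside the research team picked a starting point in a computer-generated random number table. "From this point, the corresponding random numbers were sequentially identified, ranging from 1 to 84", and after sorting, participants were assigned 1:1. No blocks, strata, surplus envelopes or central release are described.

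On concealment, section 3 says: "Group assignments were concealed within 84 consecutively numbered, identical, opaque, and sealed envelopes, which the non-research team member securely kept". On the day of enrolment, once baseline data and assessments are complete, "the principal researcher (recruiter) retrieved the envelope corresponding to the" participant's sequence number, and it is opened. The same section states that "blinding of participants, recruiters, or research intervention staff was not feasible".

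Three other provisions matter here. Section 2 says that eligible new admissions were recruited consecutively. Section 2.1 gives the attending physician the decision on inclusion (iii) and exclusion (iii), but names no decision-maker for exclusion (i), which covers "patients who are uncooperative due to impaired consciousness, cognitive dysfunction, or other factors". Section 3 has a blinded, independent assessor collect outcomes from T0 onwards.

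**The concern.** Sealed opaque envelopes hide the next allocation. They do not hide what is left in the pile from someone who has seen every earlier card and knows the starting composition. If the list holds 42 of each arm and exactly 84 envelopes exist, a simple tally tells the recruiter which arm is ahead. As the pile shrinks, that tally predicts the next allocation better and better, and the last is fixed once 83 have been opened.

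Foreknowledge matters because the recruiter acts before the envelope is opened. Someone who expects a given arm next could be more or less ready to approach a borderline patient, or to regard that patient as cooperative. If such selection rests on features that are not recorded, adjustment for measured baseline variables cannot be relied on to correct it.

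**Working it through.** **1. The plan's own figure.** Section 2.2 gives 33 per group and 20% attrition: 33 / (1 − 0.20) = 41.25, rounded up to 42 per group, and 2 × 42 = 84. The list length and arm size used below therefore agree with the plan.

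**2. Is the list exactly 42/42?** This is inferred from the numbers 1 to 84, sorting, a 1:1 ratio, 84 envelopes and 42 planned per group. Under simple randomisation an exact 42/42 split would occur with probability C(84,42)/2^84 = 0.087, and the last allocation would not be known.

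**3. Predictability of a 42/42 list.** Assume that all orders are equally likely and that the recruiter guesses the arm with more envelopes left. With r envelopes left, of which a belong to arm 1,

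P(correct) = E[max(a, r − a) / r], with a ~ Hypergeometric(84, 42, r).

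- r = 1: the probability is 1.000.
- r = 2: both envelopes are for the same arm with probability 41/83 = 0.494, so P(correct) = 0.494 × 1 + 0.506 × 0.5 = 0.747.
- Allocations 75 to 84: 0.615, 0.630, 0.630, 0.651, 0.651, 0.683, 0.683, 0.747, 0.747, 1.000. The sum is 7.04.
- A simulation of 200,000 lists gave 7.03 (SD 0.78).

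The number of final allocations known with certainty is the length of the closing run in one arm. Its expectation is 1 + 41/43 = 84/43 = 1.95.

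**4. Comparison of schemes (expected correct guesses).**

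| Scheme | Of 84 | Of last 20 | Of last 10 | 84th allocation |
|---|---|---|---|---|
| Chance (simple randomisation) | 42 | 10 | 5 | 0.50 |
| List of 84, 42/42 | 47.3 | 13.0 | 7.0 | 1.00 |
| First 84 of 120, 60/60 | 44.3 | 10.9 | 5.5 | 0.56 |
| Fixed blocks of 4, size known | 59.5 | – | 7.3 | 1.00 |

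The 120-envelope row assumes that the recruiter knows the length and split, so it is the unfavourable case for that option. For the 42/42 list, the excess over chance is 47.3 − 42 = 5.3 in the whole trial. Of this, 13.0 − 10 = 3.0 falls in the last 20 allocations and 7.0 − 5 = 2.0 in the last 10.

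**5. What this could do to the estimate.** Suppose, as an assumption, that the recruiter acts on every guess and shifts the enrolled patient's expected outcome by η in the direction of the guessed arm. The bias in the between-arm difference is (2/84) × (correct − incorrect) × η.

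- Throughout the trial: (2/84) × (2 × 47.26 − 84) × η = 0.25η.
- Last 10 only: (2/84) × (2 × 7.04 − 10) × η = 0.10η.

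With an illustrative η of 0.3 SD, these are 0.075 SD and 0.03 SD, against the planned effect of 0.8 in section 2.2.

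**6. Cost of a longer list.** The SD of one arm's count among the first 84 of 120 is √(84 × 0.25 × 36/119) = 2.52, so the SD of the arm difference is about 5. At a standardised difference of 0.62 (two-sided t-test, alpha 0.05, all 84 analysed), power is 80.2% with 42/42 and 79.6% with 37/47. That split is a difference of 10, or about two SDs.

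**The case against.** The case against is substantial, and most of it stands.

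- **The premise is inferred.** The documents do not state the list's composition, that the recruiter was told it, or that a tally was kept. The figures are what a recruiter could do, not what one did.
- **Chance accounts for most of the correct guesses.** Of the 7 in the last 10, 5 would be right anyway.
- **The plan has real safeguards.** Consecutive recruitment limits the choice of whom to approach. The attending physician judges physical capacity, communication skills and joint-affecting conditions. The baseline score is collected by a blinded assessor before the envelope is fetched from an independent custodian.
- **The method is not unusually weak.** Fixed blocks of four of known size would be more predictable, at 59.5 of 84.

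What the objection does not remove is that a tally can be made before the next patient is approached. Opening the envelope after baseline does not prevent that, and assessor blinding does not protect against selection at entry.

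A reader might infer that the recruiter applies the open-ended wording of exclusion (i), or could colour the baseline self-report. The documents do not say who applies that exclusion, and the recruiter does not collect the T0 outcomes, so neither inference is supported.

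**Conclusion.** The point holds as a minor design weakness. On the natural reading of section 3, the scheme adds about 2 correct guesses to the 5 expected by chance in the last 10 allocations, and about 5 to the 42 expected in the whole trial. On average the final two allocations are known before enrolment. This rests on three assumptions: the list is exactly 42/42, the recruiter knows this and keeps a full tally, and all 84 envelopes are used. Any effect on the estimate would probably be small beside the planned effect.

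A reader might go further and conclude that concealment failed, or that the result will be biased in a way no analysis could address. The documents do not support that. They show an opportunity but no use of it. The primary outcome is also a change from T0 (section 6.1), which partly offsets selection on baseline severity, so only selection on unmeasured features would be beyond adjustment.

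**What to change.** **If recruitment has not started:** have the custodian prepare a list longer than the target, for example 120 envelopes with 60 per arm. Use the first 84 and leave the rest unopened. Add to section 3 that the list's length and composition are not disclosed to the recruiter. The cost is 36 more envelopes, a sentence or two of text, and arms that may not be exactly 42/42, with about 0.6 percentage points of power lost at a 37/47 split. Small fixed blocks of known size should not be used as the remedy, because they are more predictable.

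**If recruitment has started:** the past tense in sections 1 to 3 leaves this unclear. Do not add to, reshuffle or renumber the envelopes, since that disturbs a concealed sequence and complicates the audit trail. Instead, report how the list was built, how many of each arm it held, and whether the recruiter knew. That costs only a short statement.
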